## 1. BACKGROUND INFORMATION

### 1.1 Name, Description and Intended Use of the Investigational Product

[REDACTED] Surgical Solution [REDACTED] is an investigational antimicrobial skin preparation containing 2% w/v chlorhexidine gluconate (CHG) and 70% v/v isopropyl alcohol (IPA) [REDACTED] for reducing the bacterial flora on patients' skin prior to surgery. [REDACTED]

[REDACTED] The product will be available in the following configurations: 10.5-mL tint and colorless, and 26-mL tint. The 26-mL tint configuration will be evaluated in the current study.

The purpose of this study is to evaluate the ability of a single preoperative preparation product to achieve similar reductions of resident flora at three different sample sites within a defined test area, [REDACTED] on the skin of the posterior torso (back region). One sample site will be in the center of the application site, a second sample will be taken halfway between (equidistant) the center and the periphery of the application site, and a third sample will be taken on the periphery of the application site.

### 1.2 Summary of Relevant Studies

[REDACTED]  
[REDACTED]  
[REDACTED] two studies were conducted to evaluate the coverage area [REDACTED] on human subjects. In study [REDACTED] the coverage area for the 26-mL applicator was evaluated and in study [REDACTED] the coverage area for the 10.5-mL applicator was evaluated. The coverage area determined in study [REDACTED] is being used as the treatment coverage area for this study. No safety concerns were identified in these studies.

Refer to the Investigator Brochure [REDACTED] for a summary of studies.

### 1.3 Risk/Benefit Summary

There are minimal anticipated adverse health risks for the participants of this study. Considerable safety and efficacy data are available for the investigational product and preclinical safety studies, [REDACTED], have been completed.

There are no direct health benefits to subjects who participate in this study.

#### **1.4 Investigational Material Application**

This study will be conducted using the tint formulation [REDACTED] in the 26-mL applicator configuration. The study product will be applied topically to intact skin of the subject's posterior torso (back region) in a defined [REDACTED] area.

The study product will be applied as intended per instructions for use (Appendix 14.2). [REDACTED]  
[REDACTED]

#### **1.5 Good Clinical Practices and Regulatory Requirements**

[REDACTED]  
[REDACTED]

This study will be conducted in compliance with the protocol, Good Clinical Practice (GCP), Declaration of Helsinki and applicable state, federal and regional regulations including 21 CFR 312 (Investigational New Drug Application), 50 (Protection of Human Subjects), 56 (Institutional Review Boards), 54 (Financial Disclosure by Clinical Investigators). And in accordance with the European Directive 95/46/EC on the protection of individuals with regard to the processing of personal data and on the free movement of such data and with the Romanian Order No 677/2001 for the protection of persons concerning the processing of personal data and free circulation of such data. And in spirit with Directive of the European Parliament and Council 2001/20/EC, and Romanian Order No. 904/25.07.2006.

#### **1.6 Study Population**

Healthy male subjects, 18 years of age or older, who meet the study inclusion/exclusion criteria are eligible for enrollment into this study.

A sufficient number of subjects will be enrolled in the screening phase to provide 18 treatment sites that meet the baseline requirements on treatment day. Subjects must satisfy all Screening Day and Treatment Day inclusion/exclusion criteria prior to collection of screening baselines and Treatment Day procedures. If the required numbers of subjects do not qualify from the initial screening group, additional subjects will be recruited, as needed. Treatment day baseline requirement is greater than or equal to  $3.0 \log_{10}$  CFU/cm^2 on each of the 3 sampling sites in the treatment site.

[figure not shown]
Each subject will be identified by a screening identification number, and a treatment number. Subject treatment numbers will not be assigned until a subject has passed the screening criteria, including screening baseline bacterial counts.

All three sampling sites (center, mid-peripheral and peripheral) on the treatment site must meet the screening baseline requirements stated in the inclusion criteria to qualify for treatment.

[REDACTED]  
[REDACTED]

## 2. STUDY OBJECTIVES

The primary objective of this study is to determine whether reductions in resident flora produced by the test product are consistent within a prepped area of skin. Sufficient number of subjects will be included for testing in order to finish with 18 evaluable subjects.

[figure not shown]

Safety will also be evaluated based on the incidence of adverse events reported during the study and assessment of skin irritation ratings.

## 3. STUDY DESIGN

[figure not shown]
### 3.1 Study Type and Methodology

This is a prospective, randomized, uncontrolled single-center study in healthy subjects.

This study will be conducted using a modification of ASTM E1173-15 Standard Test Method for Evaluation of Preoperative, Precatheterization, or Preinjection Skin Preparations. The 2-log10 reduction criteria (dry site) will be used to evaluate efficacy. Time points for sample collection are baseline (pre-prep) and 10 minutes or 13 minutes (post-prep).

Table 3.1A provides a summary of the study procedures. A schematic diagram of the study is included in Appendix 14.1.

**Table 3.1A Study Summary**

14-day Wash Out (Pre-inclusion*) Phase	Screening Phase	Treatment Phase
Perform the Informed Consent process.	Complete Inclusion/Exclusion form; check study constraints. Perform visual skin assessment.	Assign sequential subject number. Complete Inclusion/Exclusion form; check study constraints. Perform visual skin assessment. Record information on demographics.
Assign subject screening number.	Using a [REDACTED] sterile template mark back test area. Within the test area mark the 3 baseline sampling sites (center, mid-peripheral and peripheral).	Using a [REDACTED] sterile template mark back test area. Within the test area mark the 3 baseline sampling sites (center, mid-peripheral and peripheral) and the 3 post-prep sampling sites (center, mid-peripheral and peripheral).
Complete Inclusion/Exclusion Criteria form.	Collect screening baseline samples (center, mid-peripheral and peripheral) from test area.	Perform skin irritation rating.
*Prior to the scheduled Screening Phase, subjects will undergo a minimum 14-day Wash Out (Pre-inclusion) Phase.	Count screening plates to determine which subjects qualify for study.	Collect baseline samples (center, mid-peripheral and peripheral) from test area.
Review subject instructions for wash out and dispense subject personal hygiene kit	Contact eligible subjects to schedule Treatment Day (schedule for clipping 72 hours prior to treatment, if needed).	Weigh product applicator pre-application.  Apply study product.  Weigh product applicator post-application.
Schedule for clipping 72 hours prior to screening, if needed.		10-minutes [REDACTED] post-prep perform skin irritation rating.
		Per randomization, collect the post-prep samples [10-minutes [REDACTED] or 13-minutes [REDACTED]

### 3.2 Primary and Secondary Endpoints

#### Primary Endpoint:

The primary endpoint, coverage area with efficacy, is measured by  $\log_{10}$  reductions calculated by subtracting the  $\log_{10}$  number of microorganisms recovered at a specified sampling time following product application from the  $\log_{10}$  number of microorganisms recovered from the baseline sampling. Baseline samples must satisfy the inclusion criteria to be used in data analysis,  $\geq 3.0$   $\log_{10}$  CFU/cm^2 in all three sampling sites on the treatment site. The sampling time for efficacy evaluation will be specified per the randomization schedule as 10 minutes or 13 minutes post-product application.

[REDACTED]

[REDACTED]

[REDACTED]

The principal measure of safety will be the incidence of adverse events reported during the study and a summary of the skin irritation rating scores.

[REDACTED]

### 3.3 Randomization

The three post-product application sampling sites will be randomized so that 2 of the 3 sites will be sampled at one of the post-product application sample times (10 minutes or 13 minutes) and the third sampling is collected at the remaining sample time.

The randomization schedule will be provided to the study site in a separate document.

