### **3.4.3 Additional Study Supplies**

Sponsor will provide the following:

- Study Material Disposition forms
- Randomization schedule
- Data Collection Sheets (DCSs)
- Investigational product

Study site will provide the following:

- Subject Informed Consent forms, IRB/EC-approved

• [REDACTED]

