## **4. SUBJECT SELECTION**

Healthy male subjects will be recruited. A suitable number of subjects will be enrolled in the wash out (pre-inclusion), screening and treatment phase, such that a total of 18 subjects are evaluable for efficacy at completion of the study.

[REDACTED]

Subjects must follow all Subject Instructions (Appendix 14.5) and satisfy inclusion/exclusion criteria prior to enrollment into the treatment phase of the study.

All subjects will be provided verbal and written information about the study procedures, and subject instructions (Appendix 14.5). The following inclusion/exclusion criteria will be reviewed on wash out (pre-inclusion), screening and treatment day to establish eligibility for participation:

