### **5.3.3 Treatment Phase**

A sufficient number of subjects who meet the inclusion criteria will be enrolled into the Treatment Phase of the study, such that at least 18 treatment sites (back region) are evaluable at completion of the study.

The Investigator or a designee will complete the treatment Inclusion/Exclusion form. If these criteria are satisfied, complete information on demographics and perform a visual skin assessment to evaluate the condition of the test area.

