#### **5.3.3.1 Preparation of Test Areas**

A Test Site Diagram for the test area (back region) is shown in Appendix 14.7.

The test area within the back region is defined as the uppermost aspect up to the top of the scapula extending down to just above the sacrum as shown in Appendix 14.7. Using a [REDACTED] [REDACTED] sterile template, the corners of each back test area will be marked directly on the skin using a nontoxic skin marker. Six sampling sites will be numbered within the test area. The positioning and numbering of the sampling sites are standard for all subjects (Appendix 14.7). The 6 sampling sites within each back test area represent the 3 baseline (pre-prep) sites (center, mid-peripheral, and peripheral) and the 3 post-prep sample sites (center, mid-peripheral, and peripheral). The sampling sites are designated as Site 1 baseline (pre-prep) center, Site 2 baseline (pre-prep) mid-peripheral, Site 3 baseline (pre-prep) peripheral, Site 4 (post-prep) center, Site 5 (post-prep) mid-peripheral and Site 6 (post-prep) peripheral. The three post-prep sampling sites, sites 4, 5 and 6, will be randomized as the 10-minute and 13-minute post-prep sample sites.

After the back region test area is marked and sampling sites are numbered, the 3 baseline (pre-prep) samples will be collected using the cup scrub technique described in Section 6.2.1.1.

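### Must the analysis account for the randomised sampling time (10 or 13 minutes) when each location mean is compared with 2.0?

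*Combined protocol and SAP*

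**What the plan says.** Section 3.3 states that the three post-prep locations in each subject "will be randomized so that 2 of the 3 sites will be sampled at one of the post-product application sample times", 10 or 13 minutes, with the third taken at the other time; Section 5.3.3.4 repeats this. Section 5.3.3.1 names them as sites 4, 5 and 6 (center, mid-peripheral, peripheral), which "will be randomized as the 10-minute and 13-minute post-prep sample sites". The allocation list is not in the protocol: "The randomization schedule will be provided to the study site in a separate document".

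Section 3.2 defines the primary endpoint without choosing between the times: "The sampling time for efficacy evaluation will be specified per the randomization schedule as 10 minutes or 13 minutes post-product application".

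Section 8.2 lists the usual descriptive statistics for recovery, baseline and reduction. Section 8.2.1 sets a mean reduction of 2.0 at all three locations as the requirement. Neither mentions sampling time, and neither shows a redaction.

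Sections 2 and 4 aim at 18 evaluable subjects. Section 5.3.3 is slightly looser: enrolment is to be "such that at least 18 treatment sites (back region) are evaluable at completion of the study".

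**The concern.** Time is randomised within subject and crossed with location, the factor the study is about. One would expect a factor treated in this way to reappear in the analysis, and in the visible text it does not. If reductions change between 10 and 13 minutes, a location that happens to have more 13-minute samples has its mean moved for a reason unrelated to coverage.

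Two things depend on those means: the comparison of each with 2.0, and the Section 2 objective of showing that reductions are uniform over the prepared area.

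The visible text does not guarantee balance. Nothing is said about blocking, and the number analysed may exceed 18. Exclusion under 8.1 depends on treatment-day counts that are read only after 72 hours of incubation (6.2.1.1), when the product has already been applied (5.3.3.2). Even a balanced schedule can therefore lose its balance.

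**Working it through.** **Inputs.** From the document: three locations, two times in a 2:1 split, 18 evaluable subjects, threshold 2.0. Assumed, because the document gives no value: d from 0.1 to 0.5 log10; between- and within-subject SDs of 0.7 and 0.7, with other values tried; six equally likely allocation patterns (3 choices of odd site × 2 times); and, as an example of loss, 24 treated with 6 excluded at random. There is no planned figure to reproduce: the visible part of 8.3 cites a convention of 12 to 18 subjects from EN test methods and gives no SD or power.

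**Balanced schedule, 18 analysed.** 18 / 6 = 3 subjects per pattern. Each location is sampled at 13 minutes in 3 of the 6 patterns, so every location has 9 samples at each time. The error is 0.

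**Unrestricted schedule, 18 analysed.** For two locations, the difference in 13-minute indicators is +1 in two patterns, −1 in two and 0 in two, so its variance is 4/6 = 2/3.
- Location difference: SD = d × √((2/3)/18) = 0.192d.
- One location mean: SD = d × √(0.25/18) = 0.118d.

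**Balanced 24, 6 lost at random.** With the finite-population correction:
- Location difference: d × √((2/3)(24/23)/18 × (1 − 18/24)) = d × √0.00966 = 0.098d.
- One location mean: d × √(0.25(24/23)/18 × 1/4) = 0.060d.

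**Blocks of six, 19 to 23 analysed, none lost.** Only the r = n − 18 subjects beyond the third block contribute, so SD = d × √(r(2/3)(6 − r)/5) / n. This gives 0.043d, 0.052d, 0.052d, 0.047d and 0.036d for n = 19 to 23.

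SD of the chance error in a location difference (log10):

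| Case | d = 0.1 | d = 0.3 | d = 0.5 |
|---|---|---|---|
| Balanced 18 | 0 | 0 | 0 |
| Blocks, 19–23 (largest) | 0.005 | 0.016 | 0.026 |
| 24 less 6 | 0.010 | 0.029 | 0.049 |
| Unrestricted 18 | 0.019 | 0.058 | 0.096 |

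**Against ordinary sampling error.** With SDs 0.7/0.7, the SE of a location mean is √(0.49 + 0.49)/√18 = 0.233, and the SE of a location difference is √(2 × 0.49)/√18 = 0.233. In the worst row at d = 0.5, the SE of a difference rises to √(0.233² + 0.096²) = 0.252 (8%). The SE of a location mean rises to √(0.233² + 0.059²) = 0.241 (3%).

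**Effect on the 2.0 decision.** Chance that all three observed means reach 2.0, unadjusted versus adjusted for time (60,000 simulated trials of 18 analysed subjects per setting, equal true means, SDs 0.7/0.7, d = 0.5):

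| True mean | Unrestricted 18 | 24 less 6 |
|---|---|---|
| 2.1 | 0.406 vs 0.421 | 0.421 vs 0.427 |
| 2.2 | 0.596 vs 0.614 | 0.615 vs 0.620 |
| 2.3 | 0.766 vs 0.781 | 0.779 vs 0.782 |
| 2.5 | 0.951 vs 0.958 | 0.957 vs 0.959 |

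The largest gain is 0.614 − 0.596 = 1.8 points. At d = 0.1 with an unrestricted schedule, adjustment lowers the chance by 0.1 to 0.4 points. With other SDs (between/within) at d = 0.5, the largest changes for the unrestricted schedule are 3.6 points (0.5/0.5), 3.9 (0.7/0.4) and 0.7 (1.0/1.0). For 24 less 6 they are about 1 point or less.

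**Break-even.** The ratio of unadjusted to adjusted SE, unrestricted, SDs 0.7/0.7, at d = 0.1, 0.2, 0.3, 0.5 is 0.996, 1.000, 1.005, 1.026 for a location mean and 0.988, 0.999, 1.015, 1.068 for a location difference. Adjustment pays only above d of about 0.2.

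**The case for a change.** The best argument for a change is that it is nearly free. The design already randomises time, the assigned time is on the schedule, and a table by location and time needs no extra samples. Balancing the schedule cannot protect against exclusions after treatment, whereas a time term can. The objective compares locations, and that is where uneven time mixes add noise.

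These facts stand, but they do not show a defect. Exclusion under 8.1 is decided on samples taken before the product is applied, so it cannot depend on the effect of sampling time. It can unbalance the times by chance but does not bias them. Subjects have also already been screened at the same count threshold at all three sites (4.1), and nothing in the document suggests a loss as large as 6 in 24.

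A by-time table and a sentence on balance would be helpful detail, but their absence is weak evidence that they are not planned. Section 8.2 names no classification for its tables, not even location. The schedule is a separate sponsor document, and text is redacted in 3.2, 6.1, 8.1 and 8.3. An analyst holding the schedule would normally tabulate by the randomised factor.

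Applying the 2.0 criterion to model-based means would cost more than one degree of freedom. It would replace simple observed means with estimates that assume the same time effect at every location and use variance components from 18 subjects. It would lose precision if d is small. Nor would it settle how many subjects are treated or analysed.

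**Conclusion.** No change is needed. The observation is accurate: the visible analysis does not use the randomised time. But the plan contains neither a bias nor a contradiction here. A reduction at either time is the endpoint as defined in 3.2, and any chance imbalance adds noise with mean zero.

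That noise is absent with a balanced schedule and all 18 treated subjects analysed. Otherwise it is about 0.10d (24 less 6) to 0.19d (unrestricted) in SD for a location difference, or 0.05 to 0.10 log10 at d = 0.5, against a sampling SE of 0.233 for SDs 0.7/0.7. The pass probability moves by at most 1.8 points at those SDs, by up to 3.9 in the least favourable combination tried, and by 0 under balance.

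All non-zero figures rest on assumed values of d and the SDs and on an assumed schedule or loss pattern. Reporting by time and balancing the list are details that analysts and the sponsor can be expected to supply. Moving the 2.0 criterion to time-adjusted means is a trade-off with no clear gain.

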### 3.4 Study Products and Labeling

#### 3.4.1 Study Products

Investigational prep: [REDACTED] Surgical Solution, 2% w/v  
CHG/70% v/v IPA, tint formulation with 26 mL foam tipped applicator

[REDACTED]

[REDACTED] will be applied topically to intact skin of the treatment site (back region) of the subject. The prep will be applied with repeated back-and-forth strokes for 30 seconds.

Detailed instructions for application and removal of the study products are provided in the Investigational Product Application Instructions (Appendix 14.2).

#### 3.4.2 Investigational Products Labeling and Accountability

3M will label, package and ship the study products to the research facility. The [REDACTED] applicators will be provided in individual [REDACTED] packages, and labeled as below.

[REDACTED]

[REDACTED]

[REDACTED]

Sample Investigational Product Label

CAUTION: New Drug-Limited by Federal Law to Investigational Use	
For use in study EM 05-012926	
3M Health Care, [name]	
(26-mL)	Surgical Solution, Tint
Product ID: [REDACTED]	Subject Number: [REDACTED]
Lot: TBD	
Directions: Use as directed in protocol	
Warning: Contents are flammable until dry.	

3M requires Investigators to maintain accountability and adequate inventory security of the study product at all times. The Investigator or designee will:

- Document receipt of study product on the Confirmation of Release & Receipt of Clinical Supplies form (Appendix 14.3) and return the completed form to 3M,
- Store study product in a secure facility accessible only to authorized individuals,
- Dispense study product only to subjects properly enrolled into the study,
- Account for inventory and disposition using the Study Product Disposition Form (Appendix 14.4), and
- Dispose of used and unused study product as agreed upon. Once accounted for the study product may be disposed. Documentation shall be maintained concerning the disposal and will contain: the quantity of the study product disposed, the date and manner of disposal, the staff member who conducted the disposal. NOTE: Record the subject number on the package label and retain the label for inventory purposes. The used applicator can be discarded.

In addition, copies of all completed Study Product Disposition Forms and disposal records must be retained in the Investigator Study Documentation File. The originals of all Study Product Disposition Forms and disposal records must be sent to the Sponsor's Clinical Monitor.

### **3.4.3 Additional Study Supplies**

Sponsor will provide the following:

- Study Material Disposition forms
- Randomization schedule
- Data Collection Sheets (DCSs)
- Investigational product

Study site will provide the following:

- Subject Informed Consent forms, IRB/EC-approved

• [REDACTED]

### **3.5 Study Duration**

The expected duration of this study for each subject is up to 3 weeks. Each subject's participation will involve at least a 14-day Wash Out (Pre-inclusion) Phase, a 1-day Screening Phase, and a 1-day Treatment Phase. Following the Wash Out (Pre-inclusion) Phase, each subject will be required to visit the test facility on an arranged date for collection of screening baseline samples from the back region. Subjects will remain on washout until notified that they do or do not qualify for the study. Subjects whose screening baseline samples meet the requirements described in the inclusion criteria (Section 4.1) will be notified and invited to participate in the Treatment Phase of the study. The Treatment Phase will be scheduled no sooner than 72 hours from the screening baseline collections. Each subject who chooses to participate in this study will be required to return to the test facility for treatment and sample collection. Table 3.1A indicates the sequence of events throughout the study and a schematic diagram of the study is included in Appendix 14.1.

### **3.6 Study Termination/Subject Discontinuation or Withdrawal**

#### **3.6.1 Study Termination**

Conditions that may warrant the termination of the study by 3M include, but are not limited to the following:

- The discovery of an unexpected, serious, or unreasonable risk to study subjects,
- Insufficient adherence to protocol requirements,
- Failure of the Investigator to enroll subjects into the study at an acceptable rate,
- Failure of the Investigator to comply with pertinent state, federal or regional regulations or applicable privacy regulations,
- Submission of knowingly false information from the Investigator to 3M,
- Termination of IND or IRB/EC approval, or withdrawal of the IRB/EC approval,
- A decision on the part of 3M to suspend or discontinue evaluation of the investigational product.

